4.4.3 Investigational Medicinal Product Accountability

All investigational medicinal products (IMPs) required for completion of this study (RO7062931, placebo, *and* PEG-IFN) will be provided by the Sponsor. The investigational site will acknowledge receipt of IMPs, to confirm the shipment condition and content. Any damaged shipments will be replaced.

The Investigator is responsible for the control of drugs under investigation. Adequate records of the receipt (e.g., Drug Receipt Record) and disposition (e.g., Drug Dispensing Log) of the study drug must be maintained. The Drug Dispensing Log must be kept current and should contain the following information:

- The identification of the study subject to whom the study drug was dispensed (for example, subject initials and date of birth).
- The date(s) and quantity of the study drug returned by the study subject.
- All records and drug supplies must be available for inspection by the Roche Monitor at every monitoring visit.

IMPs will either be disposed of at the study site according to the study site's institutional standard operating procedure or returned to the Sponsor with the appropriate documentation. The site's method of IMP destruction must be agreed upon by the Sponsor. Local or institutional regulations may require immediate destruction of used investigational medicinal product for safety reasons. In these cases, it may be acceptable for investigational study site staff to destroy dispensed investigational product before a monitoring inspection provided that source document verification is performed on the remaining inventory and reconciled against the documentation of quantity shipped, dispensed, returned, destroyed and provided that adequate storage and integrity of drug has been confirmed.

The site must obtain written authorization from the Sponsor before any IMP is destroyed, and IMP destruction must be documented on the appropriate form.

Written documentation of destruction must contain the following:

- Identity [e.g., batch number] of investigational product[s] destroyed
- Quantity of investigational product[s] destroyed
- Date of destruction
- Method of destruction
- Name and signature of responsible person [or company] who destroyed investigational product[s].

Accurate records of all IMPs received at, dispensed from, returned to, and disposed of by the study site should be recorded on the Drug Inventory Log.

4.4.4 Post-Trial Access to RO7062931

Currently, the Sponsor does not have any plans to provide RO7062931 to study subjects after conclusion of the study.

4.4.5 Post-Trial Access to NUC/PEG-IFN

NUC or PEG-IFN are marketed drugs and commercially available. No post-study medication or drug reimbursement is provided as part of this protocol. The investigator is responsible for ensuring that consideration has been given to the post-study care of the patient's medical condition.

4.5 CONCOMITANT THERAPY AND FOOD

There are no concomitant treatment restrictions at this time as no drug-drug interactions are foreseen for RO7062931. In Part 1, there are some restrictions for healthy volunteers that should be maintained.

- Any prescribed or over-the-counter (OTC) medication, vitamins, fish oils, protein powders, including herbal remedies, taken within 2 weeks prior to first study drug administration with the exception of hormone replacement therapy (HRT) which is allowed throughout the study. Paracetamol (up to 1 g per day) will be allowed.
- However, in the event that a healthy volunteer requires additional medication during the course of the trial, this may be allowed after consultation with the Investigator and Sponsor.
- *Herbal therapy or substances (e.g. tea)/supplements/traditional Chinese medicines, as well as OTC drugs, may affect patient laboratory values. Abnormal values may lead to screening failures or patient withdrawal from study treatment. As such, patients at screening should be carefully questioned regarding such practices/habits and should be advised to refrain from them, if deemed necessary.*

It is unlikely that food will have an impact on the PK of RO7062931, however, for study subjects taking nucleosides/nucleotides food restrictions may apply. Therefore, it is suggested that both RO7062931 and the nucleosides/nucleotides be taken in the fasted state (2 hours before, or, 2 hours after a meal) during each clinic visit where RO7062931 is administered. Taking RO7062931 in a fasted state will apply to healthy volunteers and patients.

4.5.1 Permitted Therapy

Concomitant therapy includes any medication, e.g., prescription drugs, over-the-counter drugs, approved dietary and herbal supplements, nutritional supplements used by a patient from 30 days prior to screening until the follow-up visit. All concomitant medications should be reported to the investigator and recorded on the Concomitant Medications electronic Case Report Form (eCRF).

All medication administered to manage adverse events should be recorded on the Adverse Event eCRF.

4.5.2 Prohibited Therapy

As a general rule, no concomitant medication will be prohibited. All concomitant medications need be discussed with the Sponsor prior to enrolling study subjects.

For patients in Part 2c who take NUC or PEG-IFN during the study, please follow the prescribing information or the PEG-IFN Investigator Brochure, to guide as to whether concomitant medications are permitted or prohibited.

In case of doubt, the Sponsor may be contacted regarding potential prohibited concomitant medications, which may be allowed if the rationale is discussed, agreed and documented between the Investigator and Sponsor Medical Monitor.

4.5.3 Prohibited Food

There are no prohibited foods for either healthy volunteers or patients.

4.6 STUDY ASSESSMENTS

4.6.1 Description of Study Assessments

All examinations listed below will be performed according to the Schedule of Assessments tables as outlined in [Appendix 1](#) to [Appendix 14](#). At time-points when several assessments coincide, the following sequence should be followed with the PK blood sample to be taken first at the nominal time-point:

- Urine collection
- Vital signs
- ECGs
- PK, viral dynamic, safety blood sampling
- Study drug administration

4.6.1.1 Medical History and Demographic Data

Medical history includes clinically significant diseases, i.e., surgeries, reproductive status, smoking history, use of alcohol and drugs of abuse, and all medications (e.g., prescription drugs, OTC drugs, herbal or homeopathic remedies, nutritional supplements) used by the study subject within 30 days prior to the Screening visit.

For the CHB patients, the detailed HBV history will be documented, which will include date of HBV diagnosis, mode of HBV infection (if known), HBV genotype (if documented), all previous HBV treatments and outcomes of treatments, occurrence of nucleos(t)ide analogue resistance (if any), previous evaluations of cirrhosis, dates/outcomes of liver biopsies (if any).

Demographic data will include age, sex, and self-reported race/ethnicity.

4.6.1.2 Physical Examinations

A complete physical examination should be performed at baseline and include an evaluation of the head, eyes, ears, nose, throat, neck and lymph nodes, and the cardiovascular, dermatological, musculoskeletal, respiratory, gastrointestinal, and neurological systems. Further examination of other body systems may be performed in case of evocative symptoms at the Investigator's discretion.

Any abnormality identified at baseline should be recorded on the General Medical History and Baseline Conditions eCRF.

At subsequent visits (or as clinically indicated), limited, symptom-directed physical examinations should be performed. Changes from baseline abnormalities should be recorded in healthy volunteer/patient's notes. New or worsened clinically significant abnormalities should be recorded as adverse events on the Adverse Event eCRF.

Body weight will be recorded at screening and during the study. Height will be recorded at the Screening visit only. BMI will be calculated at Screening.

4.6.1.3 Vital Signs

Vital signs will be obtained after the subject has been resting in a supine position for at least 10 minutes.

Blood pressure (BP; systolic and diastolic), pulse rate and body temperature (tympanic) will be recorded at the time-points specified in the SoA tables (see [Appendix 1](#) to [Appendix 14](#)). Blood pressure and pulse rate will be performed in triplicate (can be as short as 20 seconds to 1-minute interval between measurements). The mean of three consecutive replicates will be used as the value for the defined time-point. Vital signs should be measured prior to blood draw. When possible, the same arm should be used for all blood pressure measurements.

Blood pressure and heart rate should be obtained in a quiet room at a comfortable temperature, with the subject's arm unconstrained by clothing or other material. Where possible all measurements will be obtained from the same arm and, with the same cuff size, using a well-calibrated automatic instrument with a digital readout, throughout the study (the "ideal" cuff should have a bladder length that is 80% and a width that is at least 40% of arm circumference [a length-to-width ratio of 2:1]). The study subject should be asked to remove all clothing that covers the location of cuff placement. The individual should be comfortably seated, with the legs uncrossed, and the back and arm supported, such that the middle of the cuff on the upper arm is at the level of the right atrium (the mid-point of the sternum).

4.6.1.4 Electrocardiograms

ECGs will be collected after the study subject has been in a supine position for at least 10 minutes prior to each ECG evaluation. At the specified time-points (see SoA tables, see [Appendix 1](#) to [Appendix 14](#)), 12-lead ECGs will be obtained in triplicate, i.e., three consecutive interpretable 12-lead ECGs within a 3-5-minute interval, and recorded in the case report form (CRF). Triplicate recordings should be taken for any unscheduled ECG.

All ECG recordings must be performed using a standard digital high-quality, high-fidelity ECG machine equipped with computer-based interval measurements. Automated ECG intervals (PR [PQ], QRS, QT, QTcF [to be derived in eCRF]) and heart rate (HR) will be captured or calculated, and the changes in T-wave and U-wave morphology will be documented. Changes in T-wave and U-wave morphology and overall ECG interpretation will be documented on the eCRF. T-wave information will be captured as normal or abnormal, U-wave information will be captured in two categories: absent/normal or abnormal.

For safety monitoring purposes, the investigator or designee must review, sign, and date all ECG tracings. Paper or electronic ECG tracings must be appropriately kept by the study center and must fulfill all applicable archiving requirements. The ECG intervals and interpretation will be recorded on the eCRF or may be sent electronically. If considered appropriate by Roche, ECGs may be analyzed retrospectively at a central laboratory.

The following are requirements for ECG assessments:

1. Digital ECG recordings, storage and analysis.
2. Three useful recordings must be collected without artefacts, per time-point.
3. Body position should also be consistently maintained for each ECG performed. In particular, changes in HR should be avoided. The absence of any environmental distractions (television, radio, conversation) during the pre-ECG rest and the ECG recording in the clinic must be emphasized.
4. Avoid ECG recordings within 3 hours after meals (it is accepted that this is not possible after the light breakfast which is administered prior to dosing in the fed period for the relevant cohort).
5. Strictly match timing and conditions of ECG recording to baseline. Conditions to be standardized include food intake, activity level, stressors, and room temperature.
6. If possible, the same machine, brand and model, should be used for the same study subject throughout the study.
7. ECGs should be 12-lead, recorded at 25 mm/sec for at least 10 seconds.
8. In some cases, it may be appropriate to repeat abnormal ECGs to rule out improper lead placement as contributing to the ECG abnormality.
9. ECG machines should have periodic calibration and service records (minimum once a year).

10. If any QT/QTc values > 500 msec or increases from pre-dose on Day 1 QTc > 60 msec (as provided by the machine), the site should repeat the ECG within the next 5 minutes and notify the Sponsor. If confirmed, ECG recordings should be repeated at least hourly until two successive ECGs show QTc values below the threshold value that triggered the repeated measurement.

4.6.1.5 Laboratory Assessments

All laboratory assessments will be performed at one or more central laboratories. The subsections below provide additional details specific to the type of assessments being conducted. Applicable reference ranges for the study laboratory parameters must be supplied to the Sponsor before the study starts.

Residual laboratory samples may be used to repeat laboratory tests in the event of a problem with the original sample as outlined in the SoA. Additionally, the residual samples may be used for exploratory HBV biomarker analyses to further understand disease biology and treatment impact. This may include, but is not limited to, analysis of viral and host response factors (DNA and/or non-DNA) to infection and treatment, development/validation of HBV assays, and immunogenicity analyses.

The collected samples will be destroyed no later than 5 years after the final closure of the clinical database, unless specified otherwise in the subsections below or unless regulatory authorities require specimens to be maintained for a longer time period. For patients who consented to optional RBR sample collection and analyses, any unused residual samples will be used for RBR specimen storage (see Section [4.6.1.5.7](#)).

4.6.1.5.1 Safety Laboratory Assessments

Laboratory safety tests shall be collected at time-points specified in the Schedule of Assessments (see [Appendix 1](#) to [Appendix 14](#)). Handling of residual samples is described in Section [4.6.1.5](#).

Additional blood or urine samples may be taken at the discretion of the Investigator if the results of any test fall outside the reference ranges, or clinical symptoms necessitate additional testing to monitor study subject safety. Where the clinical significance of abnormal lab results is considered uncertain, screening lab tests may be repeated before randomization to confirm eligibility. If there is an alternative explanation for a positive urine or blood test for drugs of abuse, e.g., previous occasional intake of a medication or food containing for example, codeine, benzodiazepines or opiates, the test could be repeated to confirm washout.

Additional blood and urine safety samples will also be collected at the time of a serious adverse event.

In the event of unexplained abnormal clinically significant laboratory test values, the tests should be repeated immediately and followed up until they have returned to the normal range and/or an adequate explanation of the abnormality is found. Results of clinical laboratory testing will be recorded on the eCRF or be received as electronically produced laboratory reports submitted directly from the central laboratory.

The following blood and urine samples will be collected:

- Hematology: leucocytes, erythrocytes, hemoglobin, hematocrit, platelets, differential count (neutrophils, eosinophils, basophils, monocytes, lymphocytes), mean corpuscular hemoglobin (MCH) and mean corpuscular hemoglobin concentration (MCHC).
- Blood chemistry: ALT, AST, total and indirect bilirubin, ALP, blood urea nitrogen (BUN), gamma-glutamyl transferase (GGT) (at Screening only), *glutamate dehydrogenase (GLDH)*, creatine phosphokinase (at Screening only), total protein, albumin, creatinine *and calculated creatinine clearance (using the Cockcroft Gault formula)*, glomerular filtration rate (GFR) calculated (*MDRD4 method*), uric acid, cystatin c, fasting glucose, total cholesterol, LDL cholesterol, HDL cholesterol, triglycerides, sodium, chloride, potassium, calcium, magnesium, phosphate and bicarbonate.
- Coagulation: prothrombin time (PT), International Normalized Ratio (INR), activated partial thromboplastin time (aPTT)
- Urinalysis: A mid-stream, clean catch urine specimen will be collected for dipstick analysis of protein, blood, glucose, leukocytes, specific gravity and pH. Urine will be also sent to the laboratory to perform microscopy to examine urine sediment for casts and cells. If there is a clinically significant positive dipstick result, (i.e., confirmed by a positive repeated sample), urine will be sent to the laboratory for culture. If there is an explanation for the positive dipstick result, e.g., menses, it should be recorded. Urine color may be evaluated from urinalysis or urine PK samples if considered necessary.
- Viral serology: Human immunodeficiency virus (HIV-1 Antibody, HIV-2 Antibody), hepatitis A virus (HAV IgM Antibody), hepatitis B virus (surface antigen, HBsAg), hepatitis C virus (*quantitative HCV antibody*), hepatitis D (*total HDV antibody*) (Part 2c), and hepatitis E virus (*IgM and IgG HEV antibodies*) (Part 2c).
- *Auto-antibodies at Screening: AMA, ANA, ASMA, a-TPO, anti-thyroglobulin, and anti-platelet antibodies (Part 2c).*
- Pregnancy test
For all women enrolled in the study: Blood sample for determining beta-human chorionic gonadotropin (β -HCG) at Screening. Urine pregnancy tests will be performed at specified subsequent visits. If a urine pregnancy test is positive, it must be confirmed by a blood pregnancy test.
- Alpha fetoprotein: At Screening only for HBV patients.
- *Thyroid function test: TSH (Part 2c).*

- Hormones: FSH (females only to confirm post-menopausal status, performed at Screening only).
- Drugs of abuse (urine): Cannabinoids, amphetamines, methamphetamines, opiates, methadone, cocaine, benzodiazepines, and barbiturates.
- Alcohol breath or blood test will be performed.

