5.2.1.3 Dose Modifications with PEG-IFN

The intention of Part 2c of the protocol is that patients remain on PEG-IFN until the completion of the allocated treatment period. However, it is possible that some patients will encounter transient or prolonged adverse effects or abnormal laboratory values at some juncture during their participation in the trial leading to potential need for adjustment of the PEG-IFN dosage.

If severe adverse reactions or laboratory abnormalities develop during PEG-IFN therapy, the dose should be modified until the adverse reactions abate. If intolerance persists after dose adjustment, PEG-IFN therapy should be discontinued.

When dose modification of PEG-IFN is required for adverse reactions (clinical and/or laboratory), an initial dose reduction to 135 mcg (adjustment to the corresponding graduation mark for the prefilled syringes) is recommended. Dose reduction to 90 mcg (adjustment to the corresponding graduation mark for the prefilled syringes) may be needed if the adverse reaction persists or recurs. Following improvement of the adverse reaction, re-escalation of the dose may be considered. [Table 1](#) provides guidelines for dose modifications and discontinuation of PEG-IFN for haematological laboratory abnormalities.

Table 1 PEG-IFN Hematological Dose Modifications Guidelines

Laboratory Values	Recommended Dose
ANC < 750 cells/mm ³	Reduce to 135 mcg
ANC < 500 cells/mm ³	Discontinue treatment until ANC values return to more than 1000 cells/mm ³ . Reinstigate at 90 mcg and monitor ANC.
Platelets < 50,000 cells/mm ³	Reduce to 90 mcg
Platelets < 25,000 cells/mm ³	Discontinue treatment

For patients who discontinue PEG-IFN early due to intolerability or if stopping criteria are met, then NUC and RO7062931 should be continued up to 48 weeks. The reasons for discontinuation of PEG-IFN and length of treatment duration will be recorded in the eCRF.

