Physical Examination ^k	X															X
Vital Signs ⁱ	X		X	X	X	X										X
ECG-12 lead	X															X
Hematology ^d		X		X ^b	X ^b	X ^b	X ^b		X ^b	X ^b		X ^b	X ^b	X ^b	X ^b	
Blood Chemistry ^d		X		X ^b	X ^b	X ^b	X ^b		X ^b	X ^b		X ^b	X ^b	X ^b	X ^b	
Urinalysis ^d		X		X ^b	X ^b	X ^b	X ^b		X ^b	X ^b		X ^b	X ^b	X ^b	X ^b	
TSH	X															
Viral Serology ⁿ	X															
Coagulation ^d		X		X ^b	X ^b	X ^b	X ^b		X ^b	X ^b		X ^b	X ^b	X ^b	X ^b	
Inflammatory Markers ^j			X	X	X	X	X			X						X
Autoantibodies (screening) ^o	X															
Autoantibodies (monitoring) ^m			X ^b			X ^b	X ^b		X ^b	X ^b						X ^b
ADA			X ^b		X ^b	X ^b	X ^b		X ^b	X ^b		X ^b	X ^b	X ^b	X ^b	
Alpha fetoprotein		X														
RBR DNA			X ^b													
Pregnancy Test ^f		X														

Appendix 13
Schedule of Assessments – Part 2c, QW Doses for 48 Weeks, Main Table (cont.)

Period	Discontinuation ^e	Follow Up Visit	Follow Up Visit	Follow Up Visit	Follow Up Visit	Follow Up Visit	Follow Up Visit	Follow Up Visit	Follow Up Visit	Follow Up Visit ^h
Day		week 50	week 52	week 54	week 56	week 58	week 60	week 64	week 68	week 72
		+/-3	+/-3	+/-3	+/-3	+/-3	+/-7	+/-7	+/-7	+/-7
Assessments										
Informed Consent										
Eligibility										
Demography										
Medical History										
Fibroscan ^a										
Physical Examination ^k	X									X
Vital Signs ⁱ	X									X
ECG-12 lead	X									X
Hematology ^d	X		X				X			X
Blood Chemistry ^d	X		X				X			X
Urinalysis ^d	X		X				X			X
TSH										
Viral Serology ⁿ										
Coagulation ^d	X		X				X			X
Inflammatory Markers ^j	X		X							
Autoantibodies (screening) ^o										
Autoantibodies (monitoring) ^m	X									X
ADA	X									X
Alpha fetoprotein										
RBR DNA										
Urine Kidney Biomarkers ^p	X		X							
Pregnancy Test ^f	X									X

Appendix 13
Schedule of Assessments – Part 2c, QW Doses for 48 Weeks, Main Table (cont.)

Period	Screening		Treatment Period													
	D-28 to D-4	Day -7 to -4	Day 1	week 2	week 4	week 8	week 12	week 13	week 18	week 24	week 25	week 30	Week 36	Week 42	week 48	week 49
	notime			+/-3	+/-3	+/-7	+/-7		+/-7	+/-7		+/-7	+/-7	+/-7	+/-7	
Assessments																
FSH ^g	X															
Substance Use		X														
Medications ^c			X													
PK Blood Sample ^q			7	X	2	2	7	X	2	7	X	2	2		7	X
Urine PK Sample ^r			2				2			2			2		2	
NUC PK ^s			2													
HBsAg Quantitative		X	X ^b	X ^b	X ^b	X ^b	X ^b	X ^b	X ^b	X ^b	X ^b	X ^b	X ^b	X ^b	X ^b	X ^b

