HBsAg, HBeAg Qualitative; HBsAg/Anti-HBs Complex; Anti Hbe; AntiHBs		X	X ^b		X ^b	X ^b	X ^b		X ^b	X ^b					X ^b	
Viral Genotypes			X ^b													
HBV DNA, Viral Resistance sequencing		X	X ^b		X ^b	X ^b	X ^b		X ^b	X ^b					X ^b	
HBV RNA, HBcrAg			X ^b		X ^b	X ^b	X ^b		X ^b	X ^b					X ^b	
Clinical Genotyping			X ^l													
Ambulatory Visit	X	X	X	X	X	X	X	X	X	X	X	X	X	X	X	X
Randomisation			X													
Adverse Events	X	X	X	X	X	X	X	X	X	X	X	X	X	X	X	X

Appendix 13
Schedule of Assessments – Part 2c, QW Doses for 48 Weeks, Main Table (cont.)

Period	Discontinuation ^e	Follow Up Visit	Follow Up Visit	Follow Up Visit	Follow Up Visit	Follow Up Visit	Follow Up Visit	Follow Up Visit	Follow Up Visit	Follow Up Visit ^h
Day		week 50	week 52	week 54	week 56	week 58	week 60	week 64	week 68	week 72
		+/-3	+/-3	+/-3	+/-3	+/-3	+/-7	+/-7	+/-7	+/-7
Assessments										
FSH ^g										
Substance Use										
Medications ^c										
PK Blood Sample ^q	X	X	X	X						
Urine PK Sample ^r										
NUC PK ^s										
HBsAg Quantitative	X	X	X	X	X	X	X	X	X	X
HBsAg, HBeAg Qualitative; HBsAg/Anti-HBs Complex; Anti Hbe; AntiHBs	X		X		X	X	X	X	X	X
Viral Genotypes										
HBV DNA, Viral Resistance sequencing	X		X		X	X				X
HBV RNA, HBcrAg	X		X		X	X				X
Clinical Genotyping										
Ambulatory Visit	X	X	X	X	X	X	X	X	X	X
Randomisation										
Adverse Events	X	X	X	X	X	X	X	X	X	X
Previous and Concomitant Treatments	X	X	X	X	X	X	X	X	X	X

Appendix 13

Schedule of Assessments – Part 2c, QW Doses for 48 Weeks, Main Table (cont.)

- a) For those patients who do not have a liver biopsy, Fibroscan® or equivalent test within the past 6 months from Screening.
- b) Pre -dose.
- c) Daily administration of NUC and weekly clinic SC administration of RO7062931 or RO7062931 and PEG-IFN
- d) Blood sample for RO7062931 PK and safety laboratory assessment will also be collected in the event of an SAE.
- e) Discontinuation visit: in case of early termination, a patient should be called for this visit and assessments should be performed as listed.
- f) Blood beta -human chorionic gonadotropin (β -HCG) for pregnancy test at screening, other occasions, at any time a secondary amenorrhea of more than 1 week occurs.
- g) FSH only for females and to confirm post -menopausal status.
- h) If necessary, the patients may be asked to return for additional follow-up visits.
- i) Body weight will be measured at each visit for dosing

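### Appendix 13, the 48-week schedule used when PEG-IFN is given, plans TSH at screening only, so an asymptomatic TSH change on treatment or in follow-up would be found only if the investigator chose to take an unscheduled sample

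*Combined protocol and SAP*

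**What the plan says.** Section 4.6.1.5.1 includes "Thyroid function test: TSH (Part 2c" in its list of safety samples. The entry carries no visit times; for all such tests the section says: "Laboratory safety tests shall be collected at time-points specified in the Schedule of Assessments".

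Appendix 13 is the 48-week main table for Part 2c. Its footnote c describes the treatment as "Daily administration of NUC and weekly clinic SC administration of RO7062931 or RO7062931 and PEG-IFN", so this is the schedule for patients on PEG-IFN. The TSH row has one mark, in the first screening column (Day -28 to Day -4), and no footnote marker. It is blank in the treatment period, at discontinuation and in follow-up. Hematology, chemistry, urinalysis and coagulation are marked repeatedly in the same table.

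Outside the schedule, 4.6.1.5.1 lets the investigator take extra samples "if the results of any test fall outside the reference ranges, or clinical symptoms necessitate additional testing to monitor study subject safety". For unexplained, clinically significant abnormal values it adds that "the tests should be repeated immediately and followed up until they have returned to the normal range", or until an adequate explanation is found. On PEG-IFN, Section 5.2.1.3 says: "If severe adverse reactions or laboratory abnormalities develop during PEG-IFN therapy, the dose should be modified until the adverse reactions abate". Table 1 in that section gives thresholds for ANC and platelets only.

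**The concern.** Part 2c is the only part that gives PEG-IFN, and the only part with thyroid-specific testing and exclusions: TSH, a-TPO and anti-thyroglobulin at screening (4.6.1.5.1), and exclusion criteria 4e, 4f and 6 in 4.2.3.3. Section 1.1 says that PEG-IFN carries significant safety and tolerability risks, and 4.4.2.1 gives it weekly for up to 48 weeks. Thyroid status is thus checked at entry and then drops out of the schedule. No other planned test stands in for it, because the autoantibody panel in 4.6.1.5.3 contains no thyroid antibody.

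What is at stake is the individual patient's safety. A TSH change without symptoms could go unseen while PEG-IFN continues, because no result is planned that would bring it to the investigator's attention.

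**Working it through.** The plan states no figure on this point, so there is none to reproduce. The check is a count of the Appendix 13 rows, followed by simple interval and assay arithmetic.

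**Scheduled TSH after screening**
- Treatment-period columns: Day 1 and Weeks 2, 4, 8, 12, 13, 18, 24, 25, 30, 36, 42, 48, 49 = 14. TSH marks: 0.
- Discontinuation visit: 0.
- Follow-up columns: Weeks 50, 52, 54, 56, 58, 60, 64, 68, 72 = 9. TSH marks: 0.

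**Chemistry draws that could carry TSH**
- On treatment: Weeks 2, 4, 8, 12, 18, 24, 30, 36, 42, 48 = 10.
- Follow-up: Weeks 52, 60, 72 = 3.
- Total 10 + 3 = 13, plus discontinuation. TSH is scheduled at 0 of 13.

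**Time without a scheduled TSH** (nominal; visit windows ignored)
- The single test falls between Day -28 and Day -4, and the last visit is Week 72.
- Shortest: 72 + 4/7 = 72.6 weeks. Longest: 72 + 28/7 = 76 weeks.
- The longest span divides into up to 4 weeks before dosing, up to 48 weeks on PEG-IFN, and 24 weeks after it: 4 + 48 + 24 = 76. Only the 48 weeks are scheduled PEG-IFN exposure.

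**With TSH at Weeks 12, 24, 36, 48 and 72**
- Screening to Week 12: at most 4 + 12 = 16 weeks.
- Then 12, 12 and 12 weeks to Week 48, and 24 weeks to Week 72.
- Each of these five visits is already a chemistry draw, as is discontinuation.

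**Assays**
- 5 per completer. Initial 8 patients of Cohort 10: 5 × 8 = 40. If Cohort 10 itself were expanded to 30: 5 × 30 = 150.

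**Could the results estimate a rate?** With 0 cases in 8 patients the one-sided 95% upper limit is 1 − 0.05^(1/8) = 31.2%; with 0 in 30 it is 1 − 0.05^(1/30) = 9.5%. At the initial cohort size the gain is to the individual patient, so a listing is enough.

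**The case against.** The strongest objection is that nothing in the documents says PEG-IFN affects the thyroid. The Part 2c thyroid tests and exclusions apply equally to Cohort 9, which receives no PEG-IFN, and Appendix 11 also marks TSH at screening only. Section 4.4.2.1 sends sites to the PEG-IFN Investigator Brochure, where monitoring advice may sit. This stands as a limit: the link is an inference. It does not supply a scheduled test.

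A second objection is that TSH was meant as an eligibility test, since its other uses are exclusion criteria 4f and 6. A reader might infer the opposite from a neighbouring entry, "Alpha fetoprotein: At Screening only for HBV patients", and conclude that unlabelled TSH was meant to be repeated. The documents do not support that inference. Viral serology and drugs of abuse also lack a screening-only label in 4.6.1.5.1, yet each is marked at screening only in Appendix 13.

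Third, detection does not rest on the schedule alone. PEG-IFN is given weekly in clinic, adverse events are sought at each contact (5.3.1), and extra samples are allowed for symptoms or for an out-of-range result on any test. Criteria 4e and 6 remove some patients at entry. This stands too. It covers symptomatic patients well, but leaves asymptomatic ones to the investigator's decision to sample.

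Fourth, the existing rules give little direction for TSH. The repeat rule is confined to unexplained, clinically significant values and also ends once an explanation is found, and 5.2.1.3 has no thyroid threshold. A routine TSH could therefore prompt unplanned PEG-IFN reductions, against the stated intention that patients stay on PEG-IFN. The fix has to address this.

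**Conclusion.** The point holds as a gap in scheduled monitoring. In Appendix 13 TSH is planned at 0 of 13 post-baseline chemistry draws and not at discontinuation, so an asymptomatic change during up to 48 weeks of PEG-IFN and 24 weeks of follow-up depends on an unscheduled sample. It is a cheap improvement of low to moderate priority.

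Three stronger readings are not supported:
- A reader might infer that a planned safety analysis is broken. The laboratory outcomes in 3.3.1 name hematology, chemistry, coagulation and urinalysis, so no TSH analysis was promised.
- A reader might infer that an asymptomatic change cannot be found at all. An out-of-range result on another test can lead to extra sampling without symptoms.
- A reader might take the 72.6 to 76 weeks as time at risk on PEG-IFN. It includes time before dosing and 24 weeks after PEG-IFN stops.

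The conclusion assumes that thyroid function matters on PEG-IFN. That is inferred from the Part 2c additions and cannot be checked without the Investigator Brochure. No rate of missed events is claimed, because the documents give none.

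**What to change.** - In Appendix 13, add a footnote for patients given PEG-IFN: TSH at existing chemistry draws, for example Weeks 12, 24, 36 and 48, discontinuation, and Week 72. State the same timing in 4.6.1.5.1.
- List the results with the other safety laboratory data.
- Say that the investigator judges the clinical significance of an abnormal TSH and repeats or follows it up, and that an asymptomatic TSH value alone does not trigger a PEG-IFN dose change under 5.2.1.3.
- Leave Appendix 11 (Cohort 9, no PEG-IFN) and the antibody tests as they are.

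Cost: no new visits and about 5 assays per completer (about 40 for 8 patients). There may be slightly more blood; tube and volume requirements are in the laboratory manual, which is not among the documents. Some incidental findings could still prompt PEG-IFN changes despite the wording above. The schedule needs an amendment.
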